**June 2024 – July 2025**

## **ABSTRACT**

Obesity is a disease that currently represents a great challenge from different areas, such as health, economy, society, and politics since it represents a problem with different negative consequences in each of these areas, not to mention that its prevalence worldwide is increasing. The main treatment for this problem is a lifestyle change, including diet and physical activity modifications. Specifically, nutritional treatment is usually based on balanced meal plans with caloric restriction to generate a negative energy balance. However, when a nutritional treatment is carried out, adherence to the treatment can be compromised by experiencing low satiety, or the patient's remaining hungry with the meal plan.

In this sense, some studies show evidence of increased satiety and reduced energy intake when coffee is consumed in certain doses. In the case of inulin, a decrease in appetite, an increase in GLP-1 and PYY concentrations, and even a decrease in energy intake have been reported. These effects have been attributed to certain bioactive compounds present in coffee, such as caffeine and chlorogenic acids, and in the case of inulin, to its effect on the microbiota that produces certain short-chain fatty acids, which in turn stimulate the secretion of peptides related to satiety and, being a fiber, slows gastric emptying. However, with coffee and inulin, there is contradictory evidence; in many cases, no significant changes are observed. In other words, there are still many questions to be answered.

Therefore, more scientific evidence is needed to contribute to nutritional recommendations for hunger control and satiety. Therefore, this study aims to evaluate the chemical and sensory characteristics of a coffee and agave inulin-based beverage and its effect on appetite, dietary intake, and biochemical profile in subjects with obesity. For this purpose, a randomized crossover clinical trial with an estimated n of 30 participants has been proposed to evaluate the effect of daily and two-week consumption of a coffee beverage with agave inulin in comparison with the daily and two-week consumption of a placebo beverage for two weeks (Sedes: Instituto de Nutrigenética y Nutrigenómica Traslacional (INNUGET) of the CUCS and the Bariatric and Metabolic Surgery Unit of the Civil Hospital "Juan I. Menchaca"). The measurement of appetite hormones (acetylated ghrelin, GLP-1, and PYY) will be measured by ELISA assays. Visual analog scales measure appetite sensations, and the biochemical profile is determined by dry chemistry. The study will be conducted from April 2024 to March 2025. The results of this research will be disseminated at international

congresses in a high-impact international journal, and its completion will allow several students to complete doctoral and bachelor's theses.

## **BACKGROUND**

Globally, obesity has almost tripled since 1975, as more than 650 million adults had obesity in 2016, representing about 13% of the world's population (1). In Mexico, obesity is a health problem that continues to increase, having in 2018, 75.2% of adults aged 20 years and older with overweight and obesity (2). In Jalisco, in the same year, it was reported a prevalence of obesity of 39.2% in women and 29.5% in men (3).

Obesity results from a combination of genetic, biological, sociocultural, and lifestyle factors (4). In that sense, two lifestyle habits that are very important in its development are high consumption of sugary beverages and low fiber intake. According to the National Health and Nutrition Survey (ENSANUT) 2018, 85.8% of the Mexican population over 20 years of age consumes sweetened beverages, and a large part of the Mexican population has a deficient fiber intake (2). On the other hand, appetite regulation also plays an important role in body weight control (5). Under normal conditions, hunger and satiety are well connected to allow a balance between energy consumed and energy expended; however, this does not occur in obesity (6). When there is a dysregulation in the hunger signals given by peptides such as ghrelin and in the satiety signals given by peptides such as PYY, GLP-1, and CCK, among others, or when there are alterations in the cognitive and hedonic regulation of hunger, excessive consumption of kilocalories is produced, which are stored in the form of fat, that is obesity is predisposed (7).

The increase in body fat, mainly at the visceral level, leads to metabolic alterations such as insulin resistance and dyslipidemia, increasing the risk of type 2 diabetes mellitus and cardiovascular disease (8). Therefore, to combat obesity and its consequences, the first thing recommended is a lifestyle change, such as an adequate diet, regular exercise, and psychotherapeutic interventions (7, 8). However, at present, it is a challenge to have strategies that allow successful nutritional interventions in patients with obesity. In this context, it has been observed that coffee consumption in overweight and people with obesity has been positively associated with satiety (9), reduction of body weight and hunger, and

even with a lower energy intake, partly due to mechanisms that directly or indirectly regulate the appetite mentioned above hormones (10,11).

In addition, caffeine can amplify the appetite-suppressing effect if combined with other compounds, such as fibers (12) like inulin. It has been observed that in overweight and subjects with obesity who had consumed a beverage with 24 g of inulin diluted in 300 ml of water with glucose, there was a decrease in ghrelin levels 6 hours after consumption compared to the ingestion of water with glucose (13). Inulin has also been associated with reduced hunger and energy intake (14) and increases in GLP-1 and PYY concentrations (15). However, the joint effect of coffee and inulin has not been studied, and many separate studies are inconclusive.

### **STATEMENT OF THE PROBLEM**

The accelerated increase in the prevalence of overweight and obesity in our country has generated concern and the need to generate strategies that provide solutions for its prevention and treatment (16-18). The cost of various medical complications for a person with obesity and prediabetes, if he/she does not change his/her lifestyle habits, can reach up to 1.9 million pesos in 30 years. However, if he or she modifies his or her lifestyle, in 30 years, the total expense would decrease to only 92,860 pesos (19).

In that sense, a lifestyle habit that favors the development of obesity is the consumption of sugar-sweetened beverages. According to the National Health and Nutrition Survey (ENSANUT) 2018, 85.8% of the Mexican population over 20 years of age consumes sweetened beverages, and 16.8% consume sweetened dairy beverages (17). Likewise, the obesogenic environment in which we live favors easy access to this type of beverage, and there are very few healthy beverage options within the food industry (20). On the other hand, the average fiber consumption in Mexico is 27 g per day in men and 22 g per day in women, while the daily fiber recommendation for adults is 30 g per day.

High consumption of sugar-sweetened beverages combined with low fiber intake are risk factors for developing obesity and other chronic noncommunicable diseases (21). Obesity may arise from inappropriate food choices stemming from a strong urge to eat or weak hunger inhibition (22). In addition, there are hormones and molecules involved in appetite control, and when their functionality is altered (as occurs in obesity), they lead to overeating

and the progression of obesity. Among these hormones are peptide YY (PYY), glucagon-like peptide 1 (GLP-1), and ghrelin (23,24).

Currently, it is a challenge to have strategies that allow successful nutritional interventions in patients with obesity. In this context, coffee consumption in overweight and obese people has been positively associated with satiety (25), reduction of body weight and hunger, and even with a lower energy intake, partly due to mechanisms that directly or indirectly regulate the appetite mentioned above hormones (26, 27). For its part, caffeine can amplify the appetite-suppressing effect if combined with other compounds, as is the case with fibers (28) such as inulin, which has been associated with a reduction in hunger and energy intake (29), as well as with increases in GLP-1 and PYY concentrations (30). However, the joint effect of coffee and inulin has not been studied, and many separate studies are inconclusive.

Coffee is a popular beverage. Worldwide consumption is estimated at 168 million bags of 60 kilograms (31). At the national level, Mexicans consume an average of two and a half cups daily. However, inulin is not a food consumed significantly by the Mexican population; fiber consumption generally is below the nutritional recommendations. That is why, if its effects are proven, a beverage as widely consumed as coffee in combination with agave inulin could help people with obesity regulate their appetite.

## **JUSTIFICATION**

The prevalence of obesity in 1988 in Mexico was only 9.5%, compared to 36.1% in 2018 (17), so it is necessary to start acting to improve the welfare of the Mexican population. In the search for evidence to complement a nutritional plan, the combined consumption of coffee and inulin has been proposed. Coffee consumption in our country increases by 2% each year and according to data from PROFECO (Procuraduría Federal del Consumidor), 85% of Mexicans beverage one to three cups a day (32). Agave tequilana Weber, the blue variety, is the most widely cultivated of the 117 species of agaves native to Mexico. This variety is an important source of inulin (33).

Based on previous research, these two products of the Mexican countryside have been shown, each in their own right, to provide health benefits. In the case of coffee, it has been shown to improve endurance and exercise capacity, it has antioxidant capacity, it has been associated with a lower risk of Parkinson's and Alzheimer's disease, and several studies

report a hepatoprotective effect (34); regarding appetite control and weight loss, there is still great controversy within the scientific community about its effects, especially due to the lack of randomized clinical trials. On the other hand, inulin has been shown to improve intestinal transit, lower LDL cholesterol, and be an important prebiotic for the intestinal microbiota, although its relationship with appetite control is not clear (35). These effects on regulating appetite processes such as hunger and satiety have been studied in other countries, but not in Mexico, and much less so using inulin from agave tequilana Weber.

## **OBJECTIVE**

To evaluate the chemical and sensory characteristics of coffee and agave inulin-based beverages and their effects on appetite, dietary intake, and biochemical profiles in subjects with obesity.

### **b. Specific**

1. To compare the concentrations of appetite hormones when consuming a coffee and agave inulin-based beverage vs a control beverage.
2. To compare the subjective sensations of appetite when consuming a coffee and agave inulin-based beverage vs a control beverage.
3. To compare the dietary intake when consuming a coffee and agave inulin-based beverage vs a control beverage.
4. To compare the biochemical profile when consuming a coffee and agave inulin-based beverage vs a control beverage.

## **HYPOTHESIS**

A beverage based on coffee and agave inulin modifies appetite, dietary intake, and biochemical profile in subjects with obesity.

## **METHODOLOGICAL DESIGN**

### **a. Type of study**

Double-blind randomized crossover clinical trial.

### **b. Research location**

Instituto de Nutrigenética y Nutrigenómica Traslacional (INNUGET), Centro Universitario de Ciencias de la Salud, Universidad de Guadalajara.

Unidad de Cirugía Bariátrica y Metabólica del Nuevo Hospital Civil de Guadalajara “[name]”.

### **c. Study period**

From June 2024 to July 2025

### **d. Inclusion and non-inclusion criteria**

*Inclusion criteria*

Men and women

25 to 55 years of age

BMI  $\geq$  30 and  $<$ 35 kg/m^2

Habitual coffee consumption (1 - 3 cups of 240 ml daily).

Willingness to stop consuming food and/or supplements with coffee, caffeine, and/or inulin during the study except for the intervention.

Availability of time in the mornings

Residents of the Guadalajara Metropolitan Area

Signed informed consent form

*Non-inclusion criteria*

Hypersensitivity or intolerance to coffee or inulin

Allergy or intolerance to any of the test foods

Current or within the last 6 months use of weight-loss or appetite-altering medications  
appetite altering medications

Diagnosis of diabetes, hypertension or any heart disease, thyroid disease, infectious disease (COVID-19, flu, etc.), digestive or inflammatory bowel disease or dysgeusia

Smoking

Women who are pregnant, want to become pregnant or are breast-feeding

Peri-menopausal or menopausal women

Who is on any dietary regimen for weight loss

Currently or within the last 12 months, participated in another study

Consumption of prebiotics or probiotics in the last three months

**e. Exclusion criteria**

Incomplete data and/or measurements

Lack of expected compliance (drink at least 5 of the 7 days of each week is considered compliance).

Individuals who decide to leave the study

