**f. Sample size calculation**

The information reported in the article by Rahat et al., which had a double-blind randomized crossover design, was used to calculate the sample size (13). In this study, a significant

increase in the active PYY response was found when consuming 24 g of inulin mixed with 75 g of glucose dissolved in water (increase in the area under the curve from 0 to 4 h (iAUC04) = 5.69 pmol×h/L ± 9.8 pmol×h/L), compared with consumption of only 75 g of glucose dissolved in water ((iAUC04) = 1.06 pmol×h/L ± 10 pmol×h/L) with a p=0.003.

The program G\*Power v.3.1.9.7 (36) was used for the sample size calculation, and an n=24 was obtained using the formula for dependent mean difference and considering a loss of 25% (which is common in this type of study); 30 subjects would be required for this project.

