## **METHODOLOGY**

### **Study group**

All participants will be assigned to two interventions separately, according to the random assignment sequence corresponding to the crossover design.

The interventions consist of consuming a beverage (intervention or control) 30 minutes before breakfast daily for 2 weeks, with an intermediate washout period of 2 weeks between each treatment, as shown in Figure 1. Participants will be assigned randomly to the sequence AB (intervention beverage/control) or BA (control/intervention beverage) by generating a table of random numbers in the SPSS software.

*Figure 1. Scheme of the crossover study design*

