## **Biochemical profile**

### Blood sample collection

Of the 6 sessions that the participants attend, two blood samples will be taken at the beginning and end of each phase, that is, in 4 sessions.

The first is in the morning, after 8 to 12 hours of fasting by venipuncture, and later 30 minutes after ingestion of the beverage. Two red and one purple vacutainer tubes are obtained, each with 5 ml of blood, centrifuged at 3500 rpm for 15 minutes at 4°C to separate the serum and plasma.

The serum will be used for glucose and lipid profile determinations, the plasma will be used for determining appetite hormones,

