#### Statistical analysis

Quantitative variables will be expressed as mean  $\pm$  standard deviation or median and interquartile range for descriptive statistics, and qualitative variables as frequency or percentage. The normality of the variables is evaluated with the Shapiro-Wilk test. The general linear mixed model will be used to compare the two treatments. The data will be emptied into an Excel spreadsheet to be later imported into the SPSS v.21 program for analysis, considering a value of  $p < 0.05$  as statistically significant. The graphs will be made with Graphpad software version 9.3.1.

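### The exclusion criteria remove enrolled participants for incomplete data, low compliance or withdrawal, so only compliant completers are compared

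*Protocol*

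**What the plan says.** The Protocol's Methodological design has two separate lists. Section d, "Inclusion and non-inclusion criteria", holds what is checked at screening. Section e, Exclusion criteria, has three items:

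- The first concerns missing values: "Incomplete data and/or measurements".
- The second concerns how often the beverage was taken: "Lack of expected compliance (drink at least 5 of the 7 days of each week is considered compliance".
- The third concerns withdrawal: "Individuals who decide to leave the study".

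Under Study group, participants are randomised to sequence AB or BA: "All participants will be assigned to two interventions separately, according to the random assignment sequence corresponding to the crossover design". Each beverage is taken daily for 2 weeks, with a 2-week washout between. Section f, Sample size calculation, reaches n=24 and then enrols more, "considering a loss of 25% (which is common in this type of study); 30 subjects would be required for this project". Under Blood sample collection, "two blood samples will be taken at the beginning and end of each phase, that is, in 4 sessions": one fasting and one 30 minutes after the beverage. Statistical analysis says "The general linear mixed model will be used to compare the two treatments" and names no analysis population. No section says that people meeting the section e criteria stay in the analysis.

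**The concern.** Eligibility is fully dealt with in section d, so section e can act only on people already enrolled. Compliance is observed only after the sequence has been allocated, and withdrawal and missing measurements can follow from the beverage itself. Selecting the analysed group on such events has three consequences.

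- **Bias.** Everyone retained receives both beverages, so stable personal characteristics stay balanced in the within-person contrast. That does not protect the comparison where exclusion is linked to how a person responds to, or tolerates, one of the beverages.
- **Scope.** Whether or not there is bias, the result describes only people who adhere to both beverages.
- **Precision.** A non-complier measured in both periods carries a full within-person comparison, and a person with one period carries some information. A mixed model can use both, but the exclusion rule removes them before it is fitted.

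**Working it through.** **1. The protocol's own loss figure.** 24 × 1.25 = 30, which reproduces the planned number (dividing instead, 24/0.75 = 32). The gap is 30 − 24 = 6, or 20% of 30. A 25% loss from 30 is 7.5 people. Section f does not say whether this loss includes non-compliers or people with a single missing item.

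**2. What the weekly rule selects.** There are 2 phases × 14 days = 28 drinking days in 4 weeks, and one week below 5 days fails the rule.

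| Days drunk per week | Total | Status |
|---|---|---|
| 4, 7, 7, 7 | 25 of 28 (89%) | excluded |
| 5, 5, 5, 5 | 20 of 28 (71%) | retained |

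The rule therefore does not track total intake. As an illustration only, assume that weeks are independent: if each week is compliant with probability 0.98, 0.95 or 0.90, the share passing all four is that value to the fourth power, 0.92, 0.81 or 0.66. That is about 27.7, 24.4 or 19.7 of 30, before withdrawals and incomplete data.

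**3. Samples taken before home drinking.** 4 sessions × 2 draws = 8 draws per person. The two start-of-phase sessions give 2 × 2 = 4 draws, taken before that phase's home drinking. Low home compliance in that phase cannot have affected them, yet they are lost with the person.

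**4. Precision, six non-compliers measured in both periods.** Variance is proportional to 1/n. Keeping them reduces it by 1 − 24/30 = 0.20. Dropping them widens the interval by √(30/24) = 1.118, about 12%.

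**5. Precision, six people with one period only.** This depends on the within-person correlation ρ, which the protocol does not give. It can be back-solved by assuming 80% power and a two-sided 5% level:

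- A paired t-test with n=24 then needs a standardised difference of 0.597.
- The planned difference is 5.69 − 1.06 = 4.63 pmol×h/L, so the SD of the difference is 4.63/0.597 = 7.75.
- ρ = (9.8² + 10² − 7.75²)/(2 × 9.8 × 10) = 0.69.

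Take common variance σ², 12 complete pairs per sequence, and three first-period-only participants per beverage, with period in the model. The pairs contribute information 12/[σ²(1 − ρ)] on the treatment difference. The single-period contrast has variance 2σ²/3 and adds 1.5/σ². The variance reduction is 1.5(1 − ρ)/[12 + 1.5(1 − ρ)]:

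| ρ | Reduction |
|---|---|
| 0.3 | 8.0% |
| 0.69 | 3.7% |
| 0.8 | 2.4% |

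**6. Bias, by assumption only.** Let 20% be removed, and let their effect be f times that of those kept. The retained-set estimate relative to the all-participant effect is 1/(0.8 + 0.2f) − 1:

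| f | Relative error |
|---|---|
| 0.5 | +11% |
| 1 | 0% |
| 1.5 | −9% |

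No value of f is supported by the protocol; the table shows scale, not a prediction.

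**The case against.** **Section e never says that people are excluded from the analysis.** It could be a list of reasons for ending participation, and analysis sets are often left to an SAP, which is not at hand. The wording point is true. But incomplete data is a property of the dataset, and as a criterion it makes sense only for deciding whose data are used. Nor is this a detail left open: the protocol sets a rule, and an SAP that analysed everyone would conflict with it.

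**The protocol asks about consumption.** Its specific objectives and independent variable are framed that way, so a compliant set is close to the stated question. This has force, and it is why that set should be kept. It does not justify making it the only analysis.

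**Ending with 24 is the design, not a shortfall.** Correct. The 12% is the cost of discarding usable data, not a failure to reach the target, and it assumes that all six losses are non-compliers measured twice. With one-period withdrawals the figure is about 4% at the back-solved correlation.

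**The bias figures rest on invented inputs and go both ways.** Accepted; they are illustrative.

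**The supporting examples are secondary.** A weekly minimum is a legitimate way to define regular exposure, and the detailed session timing is in a figure that could not be seen. Both points stand. The text itself does place samples at the beginning of each phase.

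**Conclusion.** The concern holds and should be fixed. As written, section e restricts the comparison to compliant completers through events that arise after enrolment, and nothing else in the protocol restores all randomised participants. The clearest fault needs no assumption about effect size: people measured under both beverages are discarded for missing a weekly threshold.

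The precision cost is 20% of variance (an interval about 12% wider) if six such people are dropped. For six one-period participants it is about 2% to 8% of variance over correlations of 0.8 to 0.3; the central 4% rests on assumed 80% power and a two-sided 5% level. The number lost, 6 to 8 of 30, takes the protocol's loss allowance as a guide, although the protocol does not say what that allowance covers. Bias is possible but not demonstrated, and its size and direction are unknown. The fault is material but not fatal, because the within-person design limits part of the damage and the remedy is simple.

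**What to change.** In section e, remove all three items as grounds for exclusion from the analysis, and say that participants remain free to withdraw from participation. In Statistical analysis, state that:

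- the main analysis includes every randomised participant with any post-beverage measurement, by the sequence randomised;
- the planned mixed model is fitted by likelihood to all available data, including data up to withdrawal, under a stated missing-at-random assumption;
- the complete set meeting the existing weekly compliance definition is a per-protocol sensitivity analysis, answering the separate question of the effect when the beverage is actually consumed.

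Requiring one post-beverage measurement is itself a mild restriction. Since a post-beverage sample is taken at the start of each phase, it should remove only those with no usable post-beverage data at all, and their number should be reported by sequence.

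The cost is a few sentences. The estimate will be smaller if non-compliers respond less, though the direction cannot be known in advance. The result will rest on missing-at-random for absent data, and one-period participants will add only modest precision. No change to the sample size follows.
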